**Please verify the length of the VAS line to be 100-mm before providing it to the subject.**

*Subject Instructions:* Ignoring any pain from insertion of the needle, please draw a single vertical line through the scale below that corresponds to the intensity (severity) of any discomfort you are feeling **right now** at the study drug injection site.

Discomfort could include stinging, burning, tingling, throbbing or pain. The further to the right you make your vertical mark, indicates the more intense discomfort you are feeling.

You should normally draw a straight line across the scale to indicate your current level of discomfort. However if you are currently feeling no discomfort, you should circle the vertical line on the left end of scale (above the word “no”). If you are currently feeling the worst discomfort possible, you should circle the vertical line on the right end of the scale.

┆

No Discomfort

┆

Worst Possible Discomfort

#### APPENDIX 4.

##### ***Delivery Site Discomfort Description and Duration Questionnaire***

*Study Personnel Instructions: All questions should be completed by the subject at 10±5 minutes following the delivery of study drug. The goal is for the subject to report if they had any discomfort and if there was discomfort, the qualitative nature and duration of discomfort associated with the delivery of study drug, ignoring any transient pain associated with the pump placement.*

*Note: If a subject is unable to physically complete the questionnaire, the subject will provide verbal responses, which will be recorded on the questionnaire by study staff. Documentation will be provided on each completed questionnaire as to who completed the form.*

*Subject Instructions: Please answer all questions below.*

1. Did you have any discomfort when the pump administered the study drug? \_\_\_\_\_ Yes      \_\_\_\_\_ No

If yes,

1a. How would you describe any discomfort you felt from the study drug? (Check **all** that apply):

- \_\_\_\_\_ Pain (e.g., throbbing, soreness, muscle ache)  
\_\_\_\_\_ Itching  
\_\_\_\_\_ Tingling, twitching or numbness  
\_\_\_\_\_ Irritation (e.g., burning, stinging)  
\_\_\_\_\_ Other (specify) :  
\_\_\_\_\_

1b. About how long after the study drug administration did the discomfort start? (please enter a number) \_\_\_\_\_ minutes

1c. In total, how long did the discomfort last? (please enter a number): \_\_\_\_\_ minutes

**APPENDIX 5. DRAIZE SCALE**

- *Study Personnel Instructions:* The modified Draize Scale as shown in the table below will be used for physical examination/rating of abnormalities at the Omnipod site.
- The injection site should be examined for formation of both erythema and edema and results recorded in the Case Report Form. Evaluations of the injection site should be performed at  $10 \pm 5$  and  $60 \pm 5$  minutes post-treatment.

Erythema Formation		Edema Formation	
Description	Score	Description	Score
No erythema	0	No edema	0
Very slight erythema Barely perceptible	1	Very slight edema Barely perceptible	1
Well defined erythema	2	Slight edema (edges of area well defined by definite raising)	2
Moderate erythema	3	Moderate edema Raised approx. 1 mm	3
Severe erythema Beet redness to slight eschar formation	4	Severe edema Raised more than 1 mm and beyond exposure area	4

Document Approvals

Approved Date: 10/8/2019, PRO-19-00084 Version 4

Approval Task Verdict: Approve	[name], ([contact]) Quality Approval 08-Oct-2019 14:50:28 GMT+0000
-----------------------------------	--

QA Approval Task Verdict: Approve	[name], ([contact]) Quality Assurance Approval 08-Oct-2019 14:51:26 GMT+0000
--------------------------------------	--

## 1 LIST OF ABBREVIATIONS

---

Abbreviation or special term	Explanation
AE	Adverse Event
ALT	Alanine Aminotransferase
AST	Aspartate Aminotransferase
AUC	Area Under the Curve
BP	Blood Pressure
BSA	Body Surface Area
CGM	Continuous Glucose Monitor
CLIA	Clinical Laboratory Improvement Act
C max	Maximum Plasma Concentration
CSGI	Continuous Subcutaneous Glucagon Infusion
CSII	Continuous Subcutaneous Insulin Infusion
ECG	Electrocardiogram
GIR	Glucose Infusion Rate
HAAF	Hypoglycemia Associated Autonomic Failure
HbA1c	Glycated hemoglobin
HBV	Hepatitis B virus
HCV	Hepatitis C virus
HIV	Human immunodeficiency virus
HR	Heart Rate
ICF	Informed Consent Form
IIR	Insulin Infusion Rate
IV	Intravenous
LSLV	Last Subject Last Visit
MedDRA	Medical Dictionary for Regulatory Activities
QTN	Quartesian LLC
PD	Pharmacodynamics
PG	PG
PGR	Positive Glucose Response
PK	Pharmacokinetic
RBC	Red Blood Cells
SAE	Serious Adverse Event

---

Abbreviation or special term	Explanation
THC	Tetrahydrocannabinol
Tmax	Time to Maximum Plasma Concentration
T1D	Type 1 Diabetes Mellitus
VAS	Visual Analog Scale
WHO	World Health Organization

---

## 2 INTRODUCTION

This document describes the planned data analyses for clinical trial XSGO-AF01 sponsored by Xeris Pharmaceuticals, Inc.

This SAP should be read in conjunction with the amended version of study protocol (XSGO-AF01, Version 4.0, dated 21-Dec 2018). Any further changes to the protocol or eCRF may necessitate updates to the SAP.

This SAP supersedes the statistical considerations identified in the protocol; where considerations are substantially different these differences will be identified. If additional analyses are required to supplement objectives described in the SAP, they may be performed and will be identified in the Clinical Study Report (CSR).

### 2.1 General Information

The proposed indication is for the management of blood glucose in type 1 diabetes patients.

Approximately 20% of the type 1 diabetes mellitus (T1DM) population suffers from recurrent severe hypoglycemia, which is of considerable consequence to the affected persons in rare cases leading to death and to the health care systems as the treatment often involves acute care and even hospitalization.

T1DM patients, with time, lose not only Langerhans' islet Beta-cell, but also Alpha-cell function leading to glucagon deficiency. Glucagon is the primary counterregulatory hormone to insulin. With fewer or no Alpha-cells, persons with diabetes who experience hypoglycemia have a delayed or insufficient glucagon response in order to both raise and normalize their blood glucose levels. Insufficient or deficient glucagon and other counter regulatory hormones response significantly increases the risk of persistent hypoglycemia in the setting of an excess exogenous insulin, that may progress to severe hypoglycemia. Hypoglycemia associated autonomic failure (HAAF) often occurs with recurrent episodes of hypoglycemia, a condition where the biologic stress response to hypoglycemia that includes loss of awareness to hypoglycemia and the corresponding loss of endogenous glucagon secretion. The pre-emptive administration of chronic exogenous glucagon, to partially replace the missing endogenous glucagon, may therefore normalize blood sugars to restore normal blood glucose over time, restore awareness, and ultimately restore autonomic function in the setting of hypoglycemia.

Xeris has used its biocompatible, non-aqueous peptide/protein reformulation technology to create a concentrated, low volume, stable glucagon formulation. Glucagon is indicated for the treatment of severe hypoglycemia in a 1 mg dose for adults and 0.5 mg for children >2 to 12 years, who are <45 kg. Additionally, Xeris glucagon has successfully been delivered for subchronic and chronic use, via the Omnipod® and vial & syringe, across multiple clinical programs.

## 3 STUDY OBJECTIVES

### 3.1 Primary Objective

The primary objective is to compare the plasma epinephrine concentration after 30 minutes of induced hypoglycemia (PG <50mg/dL) in adult T1D subjects with HAAF, who have received 4 weeks of treatment with either CSGI or placebo.

## 3.2 Secondary Objectives

### 3.2.1 Efficacy Objectives

1. Compare change in cumulative glucose infusion to maintain glucose at 50 mg/dL for the first 30 minutes after the 50 mg/dL is achieved.
2. Compare change in cumulative insulin infusion to maintain glucose at 50 mg/dL for the first 30 minutes after the 50 mg/dL is achieved.
3. Compare changes in the other counter-regulatory hormones: norepinephrine, glucagon, cortisol and growth hormone.
4. Compare changes from Induction 1 (baseline visit) to Induction 2 (visit 7, week 4) in subject responses to a validated hypoglycemia symptom questionnaire administered during induced hypoglycemia.
5. Compare changes from baseline to week 4 in CGM-derived hypoglycemia parameters of:
  - a. Proportional time spent with interstitial glucose < 70, <60 and <50 mg/dL.
  - b. Rate of hypoglycemic event episodes at plasma glucose < 70, <60, and <50 mg/dL.
  - c. Area over the curve (AOC) of the reduction from baseline in the interstitial glucose from T0 (defined as the date/time of the CSGI injection) to Tx, where x corresponds to time when interstitial glucose < 70, <60 and <50 mg/dL is achieved.
6. Compare change from baseline to week 4 in CGM-derived parameters of:
  - a. Average (mean) interstitial glucose and standard deviation
  - b. proportional time with  $70 \leq$  interstitial glucose < 180 mg/dL,
  - c. proportional time with interstitial glucose  $\geq$  180 mg/dL.
7. Describe subject reported hypoglycemic events
  - a. Symptomatic events confirmed with self-monitored glucose < 70 mg/dL.
  - b. Symptomatic events with no accompanying glucose meter reading or a reading  $\geq$ 70 mg/dL.
  - c. Asymptomatic events of self-monitored glucose < 70 mg/dL.
  - d. Severe hypoglycemia as defined by affected consciousness of hypoglycemic origin confirmed by a glucose meter reading <50 mg/dL, requiring external assistance, or prompt recovery upon hypoglycemia treatment.
8. Describe change from Induction 1 (baseline visit) to Induction 2 (visit 7, week 4) of unawareness measured by the Gold scale.
9. Describe basal, bolus and total daily insulin dose changes by treatment group.
10. Describe the time course of the endpoints (primary and secondary 1-7) from week 4 through the rest of the study.
11. Describe non-serious and serious adverse events by treatment group.
12. Describe change from Induction 1 (baseline visit) through Induction 2 (visit 7, week 4) of serum concentrations of glucagon while still on the CSGI, and serum and plasma glucagon antibodies.

## 4 ENDPOINTS

### 4.1 Primary Endpoint

Percent change from Induction 1 (baseline visit) to Induction 2 (visit 7, Week 4) in plasma epinephrine concentration after 30 minutes of induced hypoglycemia with PG <50 mg/dL. The average of the non-missing results at each step will be used in analysis.

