#### 4.2.1 Efficacy Endpoints

- Absolute change from Induction 1 (baseline visit) to Induction 2 (visit 7, Week 4) in plasma epinephrine concentration after 30 minutes of induced hypoglycemia with PG <50 mg/dL. The average of the non-missing results at each step will be used in analysis.
- Percent change from Induction 1 (baseline visit) to Induction 2 (visit 7, Week 4) in plasma epinephrine concentration after 30 minutes of induced hypoglycemia with PG <50 mg/dL by Diabetes Duration Category (<15 years, ≥15 years). The average of the non-missing results at each step will be used in analysis.
- Intravenous glucose infusion rate (GIR) [time frame: 0-30 mins induced hypoglycemia] (cumulative glucose infusion rate required to maintain insulin-induced hypoglycemia).
- Intravenous insulin infusion rate [time frame: 0-30 mins induced hypoglycemia] (cumulative insulin infusion rate required to maintain insulin-induced hypoglycemia).
- Change from Induction 1 (baseline visit) to Induction 2 (visit 7, Week 4) in other counter regulatory hormones (norepinephrine, glucagon, cortisol and growth hormone plasma concentrations) after 30 mins of induced hypoglycemia.
- Change from Induction 1 (baseline visit) to Induction 2 (visit 7, Week 4) in Neuroglycopenic Symptom Scores (if hypoglycemia present) as documented using the hypoglycemia symptom questionnaire.
- Change from Induction 1 (baseline visit) to Induction 2 (visit 7, Week 4) in Autonomic Symptom Scores (if hypoglycemia present) as documented using the hypoglycemia symptom questionnaire.
- Change from baseline to Week 4 in CGM-derived hypoglycemia parameters of:
  - Proportional time spent with interstitial glucose (IG) <70, 60, and 50 mg/dL;
  - Rate of hypoglycemic event episodes at thresholds of plasma glucose <70, 60, and 50 mg/dL.
  - Area over the curve (AOC) of the reduction from baseline in the interstitial glucose from T0 (defined as the date/time of the CSGI injection) to Tx, where x corresponds to time when interstitial glucose < 70, <60 and <50 mg/dL is achieved.
- Change from baseline to Week 4 in CGM-derived parameters of:
  - Average interstitial glucose and standard deviation;
  - Proportional time within  $70 \leq \text{interstitial glucose} < 180$  mg/dL;

- Proportional time with interstitial glucose  $\geq 180$  mg/dL.
- Change from Induction 1 (baseline visit) to Induction 2 (visit 7, Week 4) in the Gold scale as a measure of hypoglycemia awareness.

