### **5 SAMPLE SIZE**

The primary hypothesis is to evaluate change from Induction 1 (baseline visit) to Induction 2 (visit 7, Week 4) in plasma epinephrine concentration after 30 minutes of induced hypoglycemia with plasma glucose  $< 50$  mg/dL between treatment groups. Sample size is based on a closed hierarchical hypothesis test. Using this method, an alpha of 5% will be preserved for each hypothesis test where the next ordered test will only be conducted if statistical significance is achieved for that hypothesis.

Final calculations are based on 80% power and an alpha of 5%, to demonstrate a plasma epinephrine increase compared to placebo of 1.5 nmol/l given a SD of 1.34 nmol/l at an induced PG of 50 mg/dl. Sixteen subjects per treatment group (CSGI high dose, CSGI low dose, and placebo) are required based on the minimum sample size estimate for a comparison.

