## 7.10 Efficacy Analyses

### 7.10.1 Primary Endpoint

The primary endpoint is the percent change from Induction 1 (baseline visit) to Induction 2 (visit 7, week 4) in plasma epinephrine concentration after 30 minutes of induced hypoglycemia with PG < 50 mg/dL.

Hypotheses of interest:

$H_0: \mu_x = \mu_y$  vs  $H_1: \mu_x \neq \mu_y$

where the treatment comparison of interest (ranked in order of interest) is as follows:

- CSGI Combined vs placebo
- CSGI High vs placebo

- CSGI Low vs placebo
- CSGI High vs CSGI Low

For details regarding multiplicity please see section [7.10.5](#).

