### **7.10.2 Primary Efficacy Analysis**

The analysis of the primary endpoint will be performed using a two-group t-test for each treatment comparison of interest. The primary endpoint will also be analyzed, stratifying by duration of diabetes (<15 yrs, ≥15 yrs) as a secondary analysis.

A closed testing hierarchical procedure will be used to control for multiplicity. See section [7.10.5](#).

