### 7.10.5 Multiplicity

The analysis of the primary endpoint will be performed using a hierarchical hypothesis test in which an alpha of 5% will be preserved for each test. Testing will be employed in the following order:

- CSGI combined versus Placebo (if statistically significant <0.05, then the next hypothesis test will be conducted)
- CSGI high dose versus Placebo (if statistically significant <0.05, then the next hypothesis test will be conducted)
- CSGI low dose versus Placebo (if statistically significant <0.05, then the next hypothesis test will be conducted)
- CSGI high dose versus CSGI low dose

All secondary endpoints and the supportive analyses will be considered as descriptive evidence of efficacy and will be analyzed without any procedures to account for multiple comparisons.

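### SAP 5 states 80% power from nmol/l inputs that belong to absolute change, now a secondary endpoint; no power is stated for the percent-change primary test

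*SAP*

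**What the plan says.** **Primary endpoint and test.** SAP 4.1 defines the primary endpoint as "Percent change from Induction 1 (baseline visit) to Induction 2 (visit 7, Week 4) in plasma epinephrine concentration after 30 minutes of induced hypoglycemia". SAP 7.10.1 repeats the definition: "The primary endpoint is the percent change from Induction 1 (baseline visit) to Induction 2 (visit 7, week 4) in plasma epinephrine concentration". SAP 7.10.2 fixes the method: "The analysis of the primary endpoint will be performed using a two-group t-test for each treatment comparison of interest". SAP 7.10.5 orders four comparisons, each conditional on the one before, and opens with "CSGI combined versus Placebo (if statistically significant <0.05, then the next hypothesis test will be conducted".

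**Absolute change.** SAP 4.2.1 lists among the secondary endpoints "Absolute change from Induction 1 (baseline visit) to Induction 2 (visit 7, Week 4) in plasma epinephrine concentration". SAP 10 records that this was formerly primary. SAP 7.10.5 sets the standing of such endpoints: "All secondary endpoints and the supportive analyses will be considered as descriptive evidence of efficacy".

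**Sample size.** SAP 5 reads "The primary hypothesis is to evaluate change from Induction 1 (baseline visit) to Induction 2 (visit 7, Week 4) in plasma epinephrine concentration", without the word percent. It then claims 80% power at a 5% alpha for an increase over placebo of "1.5 nmol/l given a SD of 1.34 nmol/l at an induced PG of 50 mg/dl", with 16 subjects per group. Protocol 11.1.3 gives the same difference and SD. It was written when the primary endpoint (protocol 5.3.1) was change from baseline in concentration. The protocol synopsis adds a minimum of N=42, raised to 48 for attrition.

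**The concern.** A sample-size section should describe the test on which the trial's conclusion rests. Here the endpoint was changed and the power statement was not. Nanomoles per litre cannot be the unit of a percent change, so the difference and SD in SAP 5 cannot be the design assumptions for the test in SAP 7.10.2.

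The stake is interpretation. If combined CSGI v placebo is not significant, the hierarchy stops. A reader would then ask what effect the trial could have detected and would turn to SAP 5. That section offers 80% power for the primary hypothesis, but the figure was derived for a different endpoint. A reader who takes it at face value would attach the wrong sensitivity to the primary result, and nothing in SAP 5 warns against this.

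**Working it through.** **Inputs.** Difference 1.5 nmol/l, SD 1.34 nmol/l, alpha 5%, power 80%, 16 per group (SAP 5). N=42 raised to 48 (protocol synopsis). Allocation 1:1:1 (SAP 6). Two-group t-test (SAP 7.10.2). Two-sidedness is taken from the not-equal alternative in SAP 7.10.1, since SAP 5 does not state it.

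**Step 1: reproduce the plan's figure.** The standardised difference is d = 1.5/1.34 = 1.119. For a two-sample t-test the noncentrality is d × √(n₁n₂/(n₁+n₂)) on n₁+n₂−2 degrees of freedom.

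| Comparison | Noncentrality | df | Power |
|---|---|---|---|
| 13 v 13 | 1.119 × √6.5 = 2.85 | 24 | 78.2% |
| 14 v 14 | 1.119 × √7 = 2.96 | 26 | 81.3% |
| 16 v 16 | 1.119 × √8 = 3.17 | 30 | 86.5% |
| 28 v 14 | 1.119 × √9.33 = 3.42 | 40 | 91.6% |
| 32 v 16 | 1.119 × √10.67 = 3.66 | 46 | 94.7% |

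The smallest arm that reaches 80% is 14 (exact solution 13.56), and 14 × 3 = 42 matches the synopsis. A one-sided t-test would need 11 per arm, or 33 in all, which does not match. Reading N=42 as three arms of 14 is an inference, but the agreement indicates that the calculation was done in nmol/l, with 1.34 used directly as the SD of the quantity tested.

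**Step 2: try to carry it to the primary endpoint.** Percent change is 100 × (E₂ − E₁)/E₁, where E₁ and E₂ are the epinephrine values at Inductions 1 and 2. Power depends on the difference in mean percent change divided by the SD of percent change. Neither follows from 1.5 and 1.34 without the distribution of E₁ and its relation to the change. The documents give no mean or CV for E₁ and no percent-scale difference or SD.

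The direction of any difference is open too. If the change is unrelated to E₁, dividing by a variable E₁ adds spread and tends to lower power. If the change scales with E₁, dividing removes spread and tends to raise it. Nothing in the documents says which holds.

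**Step 3: what can be stated.** Fixing power at 80% and two-sided alpha at 5%, and solving the same noncentral t calculation for d:

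| Evaluable subjects | CSGI combined v placebo | Each single-arm comparison |
|---|---|---|
| 48 | 0.88 (32 v 16) | 1.02 (16 v 16) |
| 42 | 0.94 (28 v 14) | 1.10 (14 v 14) |

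These values assume normal data with equal variances. To convert one to percentage points, multiply it by the SD of percent change, which the documents do not supply.

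**The case against.** The best defence is that SAP 5 merely records how N was chosen. N=48 is fixed, so no wording in SAP 5 can alter enrolment, estimates, tests or alpha. The switch is not hidden either: SAP 10 declares it, the units are printed in SAP 5, absolute change is still tabulated (Tables 14.2.2.1.1 and 14.2.2.1.2), and percent change is loosely a change.

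Much of this stands. The switch is disclosed, and correcting the text affects no result. But SAP 5 speaks in the present tense of the primary hypothesis and does not say that its figures predate the switch. SAP 2 says that the SAP supersedes the protocol's statistical considerations and that substantial differences will be identified. None of the five items in SAP 10 mentions the basis of the sample size. The SAP itself separates percent from absolute change, so the loose wording cannot be read as covering both.

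A reader might go further and infer that the trial is underpowered for percent change, or that 48 is the wrong number. The documents support neither. As Step 2 shows, percent-change power may lie above or below 80%. Nor does the mismatch show any inflation of type I error: the t-tests and their order are the same whatever power is quoted.

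**Conclusion.** The point holds as an error in the stated power basis. The only power figure in the SAP describes a secondary, descriptive endpoint, and the test that opens the hierarchy has no stated design assumptions. For absolute change the calculation is correct and slightly conservative at the planned size: 81.3% at 14 v 14 and 86.5% at 16 v 16, taking 1.34 as the SD of the quantity tested and the test as two-sided.

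For percent change no power figure, and no direction of difference from 80%, can be derived from the documents. Under normality and equal variances, the detectable standardised difference for the first test is 0.88 to 0.94, depending on whether 48 or 42 subjects are evaluable. The correction is worth making because it concerns the primary endpoint, but it implies no change to the design.

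**What to change.** Edit SAP 5 only.

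1. In the hypothesis sentence, write percent change.
2. State that the 80% figure and the nmol/l inputs refer to absolute change, now a secondary endpoint, and do not apply to the percent-change primary test.
3. Either give a percent-scale difference and SD, with the resulting power for 32 v 16 and 16 v 16, or insert:

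> Power for percent change was not assessed. Assuming normal data with equal variances, the standardised difference detectable with 80% power at two-sided 5% is 0.88 for CSGI combined v placebo (32 v 16) and 1.02 for each 16 v 16 comparison if all 48 subjects are evaluable, and 0.94 (28 v 14) and 1.10 (14 v 14) if 42 are evaluable.

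Both sets belong in the text because the synopsis plans for attrition from 48 to 42. The second option needs no new data. It does not tell the reader the detectable effect in percentage points, but it removes a figure that does not apply.

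The cost is a few sentences. The t-tests, alpha, four-step order, tables and N=48 are unchanged.
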